4 PATIENT ENROLLMENT AND EVALUATION

4.1 APPROACHING PATIENTS, ELIGIBILITY SCREENING, AND OBTAINING CONSENT

Patients with Grade III or IV SR-aGVHD will be approached as soon as possible after diagnosis. The investigator or designee at each study site will evaluate participant eligibility. Informed consent will be obtained via a signature on the IRB or Institutional Ethics Committee (IEC) approved ICF prior to performing study specific procedures. The process of obtaining informed consent must comply with applicable ICH GCP E6 guidelines as implemented in US guidelines, GCP guidelines and national regulatory requirements.

4.2 ENROLLMENT

Once the participant has provided a signed consent and eligibility is confirmed, patients will be enrolled and randomized onto the study using the EDC system and assigned a participant identification number. Participants will be randomized to T-Guard versus ruxolitinib in a 1:1 ratio. The following procedures shall be followed:

1. An authorized user at the clinical center completes the initial screening by entering patient demographics and Segment A information (consent date, inclusion/exclusion criteria) on the Eligibility Form.
2. If the patient is eligible, a participant ID number and random treatment assignment is generated upon successful completion of the enrollment form.
3. The confirmation of randomization will be displayed for printing.

If a connection is interrupted during an enrollment session, the process is completely canceled and logged. A backup manual enrollment system will also be available to provide for short-term system failure or unavailability.

4.2.1 Treatment

Treatment should be initiated as soon as possible after randomization, ideally within 24 hours. A maximum of 72 hours (3 days) after randomization is allowable.

4.3 STUDY MONITORING

4.3.1 Follow-up Schedule

The Follow-up Schedule for scheduled study visits is outlined in [Table 4-1](#).

The timing of follow-up visits is based on the date of randomization (Day 0). A detailed description of each of the forms and the procedures required for forms completion and submission can be found in the Data Management Handbook and User's Guide.

Table 4-1: Follow-up Schedule

Assessment Time	Target Day (Days Post- Randomization)
1 week	6 days ¹
2 weeks	14 days ²
3 weeks	21 days ²
4 weeks	28 days [#]
5 weeks	35 days ²
6 weeks	42 days ²
7 weeks	49 days ²
8 weeks	56 days ²
10 weeks	70 days ³
90 days	90 days ³
6 months	180 days ⁴

¹Target day window for Ruxolitinib arm only is +/-3 days (see section [2.5.1.5](#) for guidance on T-Guard infusion delays)

²Target day window is +/- 3 days

³Target window is +/-14 days

⁴Target window is +/-28 days

[#]Target day window is +/-2 days

Data Collection: The investigator or site designee will enter data collected using an electronic data capture system. In the interest of collecting data in the most efficient manner, the investigator or site designee should transcribe data (including laboratory values, if applicable) in the eCRF in a timely manner after the participant visit unless otherwise noted. The BMT CTN DCC will be reviewing form submission regularly and will follow-up to assure data is submitted promptly.

The investigator or site designee is responsible for ensuring that all data in the eCRFs and queries are accurate and complete and that all entries are verifiable with source documents. These documents should be appropriately maintained by the site.

The monitor will verify a subset of the data in the eCRFs with source documents and confirm that there are no inconsistencies between them.

Criteria for Forms Submission: Criteria for timeliness of submission for all study forms are detailed in the Data Management Handbook and User's Guide. Forms that are not entered in the EDC system within the specified time will be considered delinquent. Transplant Centers can view past due forms via the EDC system. A missing form will continue to appear until the form is entered into the EDC system, or until an exception is granted and entered into the Missing Form Exception File, as detailed in the Data Management Handbook and User's Guide.

Reporting Participant Deaths: The Recipient Death Information must be entered into the EDC system within 24 hours of knowledge of a participant's death even if the cause of death is unknown at that time. Once the cause of death is determined, the form must be updated.

Study Documentation: Study documentation includes, but is not limited to, all eCRFs, workbooks, source documents, monitoring logs and appointment schedules, sponsor-investigator correspondence, and signed protocol and amendments, IRB/IEC correspondence and approved current and previous consent forms and signed participant consent forms.

Source documents include all recordings of observations or notations of clinical activities and all reports and records necessary for the evaluation and reconstruction of the clinical research study. The original recording of an observation should be retained as the source document. If the original recording of an observation is the electronic record, that will be considered the source.

Clinical Study Monitoring: The Sponsors or delegated Clinical Research Organizations (CROs) are responsible for monitoring the clinical study to ensure that the participant's human rights, safety and well-being are protected, that the study is properly conducted in adherence with the current protocol and GCP and study data reported by the investigator/sub-investigator are accurate and complete, and that they are verifiable with study-related records such as source documents. The Sponsors or delegated CROs are responsible for assigning study monitor(s) to this study for proper monitoring. The protocol will be monitored in accordance with planned monitoring procedures.

Center for International Blood and Marrow Transplant Research (CIBMTR) Data

Reporting: Centers participating in BMT CTN trials must register pre and post-transplant outcomes on all consecutive HCTs done at their institution during their time of participation to the CIBMTR. Registration is done using procedures and forms of the Stem Cell Transplant Outcomes Database (SCTOD) (Note: Federal legislation requires submission of these forms for all US allotransplant recipients). CIBMTR post- transplant Report Forms must continue to be submitted for all participants enrolled on this trial. Long-term follow-up of US participants on this study will continue through routine CIBMTR mechanisms. Centers within Europe participating in BMT CTN 2002 should report additional data, including long-term follow-up, per European requirements.

4.3.2 Assessments

Assessment and/or reporting of the following is required for participants enrolled on this study. All assessments are considered standard-of-care unless identified below by “*”. Assessments indicated by “**” are for research purposes.

Prior to Enrollment

The following pre-enrollment assessments must be completed prior to enrolling the participant in the EDC system and within the designated timeframe listed below.

1. Complete aGVHD staging and grading information including assessments of rash, diarrhea, nausea/vomiting, and bilirubin, within 24 - 72 hours prior to enrollment. Biopsy results of involved tissue, if performed as SoC, should also be reported.
2. Medical history within 24 – 72 hours prior to enrollment.

3. Albumin and CK level within 24 – 72 hours prior to enrollment.
4. Complete blood count (CBC) with differential and platelet count within 24 - 72 hours prior to enrollment.
5. Renal function (blood urea and/or blood urea nitrogen, creatinine) within 24 - 72 hours prior to enrollment.
6. Schistocytes, haptoglobin and LDH within 24 - 72 hours prior to enrollment.
7. Pregnancy test (urine or serum) for females of child-bearing potential within 30 days prior to enrollment.
8. Recording of Concomitant medications starting at 7 days prior to randomization

Baseline Assessments

Baseline assessments listed below must be completed at time of enrollment and prior to the first dose of study therapy unless otherwise specified.

1. Physical exam including height and weight, participant disease/transplantation baseline variables
2. Karnofsky Performance Status (may be completed pre- or post-enrollment)
3. Baseline patient-reported outcome measures (see APPENDIX E)
4. Peripheral blood for EBV and CMV viral load (within 72 hours prior to first dose of study drug)
5. CBC with differential and platelet count
6. Recording and review of Concomitant medications
 - a. For all immunosuppressant agents, the overall start and stop date will be captured. For agents where dosing is tapered in response to drug levels, the medication dosing will not require reporting.
 - b. Dosing for corticosteroids will be captured for all dosing changes.
7. Peripheral blood* for Peripheral Blood Mononuclear Cells (PBMC) testing (See APPENDIX B)
8. Peripheral blood* for Flow Cytometry and Immune Profiling (See APPENDIX B)
9. Peripheral blood* for humoral response (ADA) testing for T-Guard arm only(See APPENDIX B)
10. Peripheral blood* and urine sample* for GVHD biomarker testing (See APPENDIX B)

T-Guard Treatment Assessments

The assessments listed below are to be completed on days of treatment for participants randomized to receive T-Guard. Assessments should be done prior to infusion, unless otherwise specified.

1. Complete aGVHD staging and grading information including assessments of rash, diarrhea, nausea/vomiting, and bilirubin on Days of infusion
2. Vital signs (temperature, pulse, respiratory rate, blood pressure) on Days of infusion . Vital signs should be taken just before starting the infusion, 15 and 30 minutes after the start of the infusion, then every 30 minutes during the infusion, and at 1 hour post-infusion. Deviation of +/- 5 minutes may occur for all vital sign collection timepoints.
3. Albumin on Days of infusion
4. CBC with differential and platelet count on Days of infusion

5. Renal function (blood urea and/or blood urea nitrogen, creatinine) on Day of 4th infusion
6. Schistocytes, haptoglobin and LDH on Day of 4th infusion
7. Peripheral blood for EBV and CMV viral load on Day of 4th infusion
8. Recording and review of Concomitant medications on Days of infusions
 - a. For all immunosuppressant agents, the overall start and stop date will be captured. For agents where dosing is tapered in response to drug levels, the medication dosing will not require reporting.
 - b. Dosing for corticosteroids will be captured for all dosing changes.
9. Recording of AE/SAEs as described in Section 4.4 Adverse Event Reporting
10. Recording of infections
11. Peripheral blood* for humoral response (ADA) on Day of 4th infusion (See APPENDIX B)
12. Peripheral blood* for PK at the following timepoints (See APPENDIX B):
 - a. 1st infusion: pre-infusion and at 4, 5, 6, 8, and 24 hours after start of infusion
 - b. 2nd infusion: pre-infusion and at 4 and 24 hours after start of infusion
 - c. 3rd infusion: pre-infusion and at 4 and 24 hours after start of infusion
 - d. 4th infusion: pre-infusion and at 4, 6, 24, and 48 hours after start of infusion

Pre-infusion samples should be drawn prior to T-Guard administration. A window of +/- 15 minutes is allowed for samples drawn at 4 hours after the start of infusion, a window of +/-30 minutes for the sample drawn 5, 6, or 8 hours after the start of infusion, and a window of +/- 1 hour for samples drawn 24 or 48 hours after the start of infusion. Every effort should be made to collect PK samples at all timepoints; however, *no* PK sampling is required on weekend days. Please refer to Section 2.5.1.5 for more information regarding T-Guard infusion delays.

Post-Randomization Assessments

The following assessments and observations must be completed at the timepoints designated below.

1. Complete aGVHD staging and grading information including assessments of rash, diarrhea, nausea/vomiting, and bilirubin at Days 0, 6, 14, 21, 28, 35, 42, 49, 56, 70, 90, and 180
2. cGVHD evaluation (if present) Day 28, 56, 90, and 180
3. Blood pressure at Days 0, 6, 14, 21, 28, 35, 42, 49, 56, 70, 90, and 180
4. Albumin at Days 0, 6, 28, 56, 90, and 180
5. CBC with differential and platelets at Days 0, 6, 14, 21, 28, 56, 90, and 180
6. Renal function (blood urea and/or blood urea nitrogen, creatinine) on Days 6, 14, 21 and 28
7. Schistocytes, haptoglobin and LDH on Days 6, 14, 21 and 28
8. Karnofsky performance status at Days 28, 56, 90, and 180
9. Peripheral blood for EBV and CMV viral load at Days 6, 14, 21, 28, 35, 42, 49, 56 and 180
10. Recording and review of Concomitant medications other than immunosuppressant agents will be collected starting at 7 days prior to randomization through 30 days post-last treatment dose for T-Guard and through Day 44 for ruxolitinib. Recording of all systemic immune suppressive therapy (as appropriate: tacrolimus, cyclosporine, etc.), as well as topical agents, and all anti-infectives used for prophylaxis or treatment at Days 6,

14, 21, 28, 35, 42, 49, 56, 70, 90, and 180

- a. For all immunosuppressant agents, the overall start and stop date will be captured. For agents where dosing is tapered in response to drug levels, the medication dosing will not require reporting.
- b. Dosing for corticosteroids will be captured for all dosing changes.

11. Patient reported outcomes at Days 28, 90 and 180 (see APPENDIX E)

12. Recording of toxicities on Days 56, 70, 90, and 180

13. Recording of AE/SAEs as described in Section 4.4 Adverse Event Reporting

14. Recording of infections through Day 180

15. Recording of primary disease relapse through Day 180

16. Peripheral blood* for Peripheral Blood Mononuclear Cells (PBMC) testing at Days 14, 28, 56, and 180 (See APPENDIX B)

17. Peripheral blood* for ADA testing for T-Guard arm only at Days 14, 28, 90, and 180

18. Peripheral blood* for Flow Cytometry and Immune Profiling at Days 14, 28, 56, and 180 (See APPENDIX B)

19. Peripheral blood* and urine sample* for GVHD biomarker testing at Days 6, 14, and 28 (See APPENDIX B)

Please refer to APPENDIX K at the end of the protocol for the Schedule of Assessments tables.

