2.5.1.4 Dose and Administration of T-Guard

It is strongly recommended all doses of T-Guard be received while the participant is hospitalized. T-Guard will be administered over 4 hours every 2 calendar days on Days 0, 2, 4, and 6, at a dose of $4\text{mg}/\text{m}^2$ BSA (not to exceed a dose of 10mg). Dosing should be per the following steps:

- Measure the participant's actual body weight (ABW)
- Determine the ideal bodyweight
 - Males IBW = $50\text{kg} + 2.3\text{kg}$ for each inch over 5 feet (or for each 2.5cm over 1.52m)
 - Females IBW = $45.5\text{kg} + 2.3\text{kg}$ for each inch over 5 feet (or for each 2.5cm over 1.52m)
- When the participant's body weight is more than 125% of their IBW, the BSA calculation is based on the adjusted ideal body weight (AIBW; formula 2) as is usual practice for IV treatment (e.g. chemotherapy).

For participants weighing more than 125% of their Ideal Body Weight, calculate the Adjusted Ideal Body Weight: $\text{AIBW} = \text{IBW} + [(0.25) \times (\text{ABW} - \text{IBW})]$

- Use the (adjusted ideal) body weight to determine BSA per the Mosteller calculation

$$BSA(m^2) = \sqrt{\frac{HEIGHT(cm) \times WEIGHT(kg)}{3600}}$$

- Multiply BSA with 4mg/m² as the T-Guard dose. If the participant's BSA is more than 2.5m², the dose calculation should use 2.5m². This dose will be maintained for all infusions (dose adjustments for changes in weight during the treatment period will not be made).

Premedication with antihistaminica (e.g., diphenhydramine 50mg by mouth or 25mg IV, clemastine 2mg IV) is strongly recommended, 20-60 minutes prior to each dose. Premedication with acetaminophen is permitted.

It is recommended that T-Guard be infused via a central catheter using a dedicated line or can be administered via a peripheral line, if needed. If a multi-lumen central venous catheter is used, T-Guard and crystalloid or total parenteral nutrition should be administered through different lumens of the catheter. PK samples should be drawn from the central catheter using a different lumen than the lumen used for infusion.

Before the infusion, connect the syringe with the in-line filter and luer-lock extension tube to a central venous catheter (recommended) or peripheral line. The contents of the syringe will then be administered by means of an automated infusion device, over a period of 4 hours. Once the infusion syringe is empty, the administration tubes should be flushed.

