Vital signs (temperature, pulse, respiratory rate, blood pressure), should be checked at the following timepoints with each infusion: just before starting the infusion, 15 minutes after the start of the infusion, 30 minutes after the start of the infusion, then every 30 minutes during the infusion, and at 1-hour post-infusion. Deviation of +/- 5 minutes may occur for all vital sign collection timepoints.

Infusion-related reactions are a potential risk with this medication. If the participant experiences a grade 3 or 4 infusion related reaction, the infusion should be held, and the reaction managed per institutional standards. Once the reaction has resolved the infusion can be restarted at half the rate. Subsequent infusions should be managed with an escalation in premedication based on type of reaction and initiated at the half rate. After 15 minutes, if no reactions are noted, then the infusion rate can be escalated to the full rate as tolerated.

Participants should receive a maximum of 4 doses. The minimal interval between doses is 2 days (the start of infusion should be no less than 40 hours from the start of the previous infusion). If toxicity occurs, then dosing should be delayed until toxicity improves, but all dosing must be completed within 14 days. Infusions of T-Guard that exceed 4 hours are not considered deviations. Pauses in the infusion due to a participant reaction need to be documented.

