2.5.1.5 T-Guard Infusion Delays

In the event dosing must be delayed due to occurrence of toxicity, the protocol allows up to 14 days to receive all four infusions. If the infusion visits are delayed, then the assessments for each infusion should still be done.

If an infusion is delayed to Day 11-13, the Day 14 visit can be combined as appropriate respecting the 3-day window for the Day 14 visits. However, it's ideal for the assessments to be completed on Day 14. If an infusion is delayed and occurs on Day 14, then the infusion day assessments must be done while the Day 14 assessments can either be done on the same day or on another day within window, per investigator discretion. If all assessments for the infusion (Day 4 or 6) and Day 14 are combined to be completed on the same day, Peripheral blood for anti-drug-antibodies (ADA), Peripheral blood for GVHD biomarkers, and a urine sample for GVHD biomarkers are to be collected prior to infusion. If the samples can't be drawn pre-infusion, they may be collected the day after.

Centers are to be mindful of the max blood draw volumes per day for participants and to combine sample collection to avoid unnecessary needle sticks.

There should be at least 4 but preferably 7 days between the biomarker samples.

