3.4.2.1 Time to Complete Response

The time from randomization to first observation of CR will be evaluated.

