5.6.3 Time to Complete Response (CR)

The time from randomization until first attaining a CR will be described for each treatment arm using the Aalen-Johansen estimator, with death and additional systemic treatment for aGVHD treated as competing risks. Estimates and 95% CIs of the cumulative incidence of CR will be

provided at Days 28 and 56 post-randomization. The cause-specific hazards of CR will be compared between arms using a Cox proportional hazards model with adjustment for the stratification factors and for acute GVHD grade at randomization (Grade III vs. IV).

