Assessment	Prior to Randomization	Day of Randomization and Prior to Treatment	Treatment and Follow-up									
			0	6	14	21	28	35	42	49	56	70
Target study day	-1	0	0	0	6	14	21	28	35	42	49	56
Window (days)	-3 to -1	0	0 to 3	+/-3	+/-3	+/-3	+/-2	+/-3	+/-3	+/-3	+/-3	+/-7
Study drug initiation ²		X										
Acute GVHD evaluation, including bilirubin	X	X	X ³	X	X	X	X	X	X	X	X ⁴	X ⁴
Chronic GVHD evaluation							X			X		X
Medical History	X											
Physical exam (weight and height)		X										
Blood pressure		X	X	X	X	X	X	X	X	X	X	X
CBC with differential and platelet count	X	X	X ³	X	X	X	X	X	X	X	X	X
Albumin	X		X	X	X	X	X	X	X	X	X	X
Renal function (blood urea and/or blood urea nitrogen, Creatinine)	X		X	X	X	X	X	X	X	X	X	X
Schistocytes, haptoglobin and LDH	X		X	X	X	X	X	X	X	X	X	X
CK levels ⁵	X											
Peripheral blood for CMV and EBV viral load		X	X	X	X	X	X	X	X	X	X	X
Pregnancy test (if applicable) ⁶	X											
Karnofsky performance status	X						X				X	X
Peripheral blood for GVHD biomarkers REG3 α and ST2 7	X		X	X	X	X	X					
Peripheral blood mononuclear cells (PBMC) 7	X			X	X	X	X			X	X	X
Peripheral blood for immunophenotyping 7	X			X	X	X	X			X	X	X
Urine sample for GVHD biomarker 3-IS 7	X	X	X	X	X	X	X					
Concomitant medication review ⁸	X	X	X	X	X	X	X	X	X	X	X	X
AE/SAE assessment ⁹		X	X	X	X	X	X	X	X	X	X	X
Toxicity assessment									X	X	X	X
Patient-reported outcomes: PROMIS		X							X	X	X	X

Assessment	Prior to Randomization	Day of Randomization and Prior to Treatment	Treatment and Follow-up											
			0	6	14	21	28	35	42	49	56	70	90	180 ¹
Target study day	-1	0	0	6	14	21	28	35	42	49	56	70	90	180 ¹
Window (days)	-3 to -1	0	0 to 3	+/-3	+/-3	+/-2	+/-3	+/-3	+/-3	+/-3	+/-3	+/-7	+/-7	+/-7
Infection monitoring			Reporting of infections at time of occurrence from time of enrollment through Day 180											
Primary disease relapse reporting			Reporting of relapse at time of occurrence from time of enrollment through Day 180											

¹Participants will be followed for survival post Day 180

²Refer to the pharmacy manual for details of ruxolitinib schedule

³Assessment does not need to be repeated if treatment starts on same day as randomization

⁴Patients will be instructed to contact the site when their aGVHD symptoms worsen in between visits Day 70, 90 and 180

⁵If patients experience muscle pain, then a serum CK should be performed

⁶May be performed within 30 days of enrollment

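### Time to CR counts the first observed CR, but T-Guard participants are staged on infusion days that ruxolitinib participants do not have; limit this secondary endpoint to visits common to both arms.

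*Combined protocol and SAP*

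**What the plan says.** Both arms follow the post-randomization staging list in Section 4.3.2: "bilirubin at Days 0, 6, 14, 21, 28, 35, 42, 49, 56, 70, 90, and 180". The T-Guard arm has a second list for treatment days, which adds "Complete aGVHD staging and grading information including assessments of rash, diarrhea, nausea/vomiting, and bilirubin on Days of infusion". Section 2.5.1.4 gives the planned days: "T-Guard will be administered over 4 hours every 2 calendar days on Days 0, 2, 4, and 6". In Table K-2, the ruxolitinib row "Acute GVHD evaluation, including bilirubin" has no column between treatment start (target Day 0) and Day 6, and none between Day 6 and Day 14.

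The T-Guard days can move. Sections 2.5 and 4.2.1 allow treatment to start up to 72 hours after randomization. Section 2.5.1.4 says "all dosing must be completed within 14 days" when toxicity delays an infusion, and Section 2.5.1.5 adds: "If the infusion visits are delayed, then the assessments for each infusion should still be done". Table 4-1 gives a window of plus or minus 3 days for the Day 6 visit to the ruxolitinib arm only.

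Section 3.4.2.1 defines the endpoint: "The time from randomization to first observation of CR will be evaluated". Section 5.6.3 reports cumulative incidence of CR at Days 28 and 56 and states: "The cause-specific hazards of CR will be compared between arms using a Cox proportional hazards model". The CR definition in Section 3.1 scores a given day and asks for no confirmation or minimum duration. No section restricts the endpoint to shared visits or treats the CR date as interval-censored.

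**The concern.** A first-observed event depends on how often one looks. On the planned schedule, T-Guard has two looks that ruxolitinib lacks, Days 2 and 4. If treatment starts on Day 3, an undelayed course falls on Days 3, 5, 7 and 9. Delayed infusions can place further looks between Days 6 and 14. A CR that begins between shared visits can therefore be dated sooner under T-Guard, and a CR that comes and goes between them can be counted in that arm and missed in the other.

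A rapid response is part of the stated case for T-Guard (the summary closing Section 1.2.3, and Section 1.4), and time to CR is the endpoint that would support it. The extra stagings are open-label site assessments, because the blinded committee in Section 3.6 reviews Day 28 response only. An earlier CR under T-Guard could then be disputed as an effect of the visit schedule.

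**Working it through.** **The plan's own figures.** No power, hazard ratio or sample size is stated for time to CR. The sample size used here is the plan's: 123 per arm, CR rates 43% and 26%, one-sided 2.5%. As a check on those inputs, the pooled standard error is √(2 × 0.345 × 0.655 / 123) = 0.0606 and the unpooled one is √((0.43 × 0.57 + 0.26 × 0.74) / 123) = 0.0596. Power is Φ((0.17 − 1.96 × 0.0606) / 0.0596) = 80.5%, against 80.56% in Table 5-2.

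**Simulation with equal drugs.** From the documents: the staging days above, 123 per arm, 15% mortality by Day 30 (Section 5.3.2 expects 15–20%), and salvage treatment from Day 7 (Section 2.5.3.4). Assumed, because the documents do not say: half of participants reach CR; onset is lognormal (log-SD 0.7) with median 8, 12 or 18 days; CR is lost at 0, 25 or 50% per week; and the salvage rates. The Cox model uses Efron ties. All delayed means that every T-Guard participant is infused on Days 0, 4, 8, 12 or on Days 3, 5, 7, 9, with calendar visits kept, so it is an upper bound. Ranges run over the three onset medians.

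| CR loss per week | T-Guard infusions | Hazard ratio | One-sided rejection for T-Guard | Gain in observed CR by Day 28 (points) |
|---|---|---|---|---|
| 0% | on schedule | 1.00–1.02 | 2.5–2.8% | about 0 |
| 0% | all delayed | 1.01–1.09 | 2.4–6.2% | 0–0.5 |
| 25% | on schedule | 1.00–1.04 | 2.3–3.6% | 0–0.5 |
| 25% | all delayed | 1.07–1.19 | 4.3–13.2% | 1.3–3.4 |
| 50% | on schedule | 1.01–1.09 | 2.6–5.5% | 0–1.5 |
| 50% | all delayed | 1.12–1.32 | 6.8–24.7% | 2.2–6.1 |

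On schedule, the median time to first observed CR is the same in both arms. Adding visit windows (ruxolitinib Day 6 plus or minus 3 days) widens the hazard ratio range to 0.99–1.14, with rejection up to 8.3% and a gain of up to 2.8 points.

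**Which loss rates fit the plan?** Take 45% ever reaching CR, exponential onset with mean a days and exponential duration with mean b days. The share in CR on Day 28 is 0.45 × [λ/(μ − λ)] × (e^(−28λ) − e^(−28μ)), with λ = 1/a and μ = 1/b. If a = b, it is 0.45 × 28λ × e^(−28λ).

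- a = 14, b = 14: 0.45 × 2 × e^(−2) = 12%
- a = 8, b = 14: 0.45 × 2.333 × (0.1353 − 0.0302) = 11%
- a = 8, b = 7: 0.45 × 7 × (0.0302 − 0.0183) = 4%
- sustained CR: 0.45 × (1 − e^(−2)) = 39% for a = 14, and 0.45 × (1 − e^(−3.5)) = 44% for a = 8

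Section 5.1.5 plans on 43% and 26%, and Section 5.2.1 takes 20% as the historical rate. Mean durations of 7 to 14 days are far below all three. The 50%-per-week rows share this problem: for a CR beginning on Day 8, 0.50 × 0.5^(20/7) = 7%. At 25% per week the same rough sum is 0.50 × 0.75^(20/7) = 22%, before deaths and salvage, which is not far from the ruxolitinib rate.

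**Restricting to shared visits.** Counting CR only at visits common to both arms, on exact visit days, gives hazard ratios of 0.99–1.01 and rejection of 2.0–2.6% in all nine scenarios.

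**The case against.** The strongest reply is that the bias is minor. Only two looks are unshared on schedule, and a lasting CR that begins by Day 4 is still seen at the ruxolitinib Day 6 visit. Section 1.2.3 suggests that responses last: in the randomized ruxolitinib trial, response was 62% at Day 28 and 40% was maintained to Day 56. Read crudely, that is a mean duration of 28 / ln(62/40) = 64 days. These are overall responses, so they are only a proxy for CR. With a mean of 65 days, exponential onset and 30% of T-Guard participants delayed (an assumed share), the hazard ratio is 1.05 to 1.09, rejection about 4–6%, and the Day 28 gap about 0.7 points. This stands as a limit on size, not as a defence of the definition.

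A reader might infer that T-Guard will show CR more often even with equal drugs, or that hazard ratios of 1.1 to 1.3 should be expected. The documents support neither. Extra detection needs a CR to be lost, or a death to occur, before the next shared visit. The larger ratios need early onset with rapid loss, or widespread delays, and the documents give no delay rate. A delay may also move the T-Guard Day 6 staging instead of adding one, since Table 4-1 exempts that arm from the Day 6 window and refers to Section 2.5.1.5.

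The consequence is limited too. Section 5.6 describes only OS as alpha-protected among the secondary comparisons, and the primary endpoint is assessed at a shared Day 28 visit with blinded review.

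**Conclusion.** The point holds as a modest, avoidable tilt toward T-Guard in one secondary endpoint. Dating is earlier by construction, while extra detection is conditional. If CRs last, the hazard ratio with equal drugs is about 1.00 to 1.09, and the upper end requires delays in every T-Guard participant or similarly unfavourable inputs. Intermediate durability combined with universal delay could reach 1.19. Figures above that rest on CR durations that conflict with the planned Day 28 rates. All sizes depend on assumed onset, loss and delay rates. The primary endpoint and the alpha-protected OS comparison are not affected. The change is worth making because delays and durability cannot be known in advance and the remedy is cheap.

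**What to change.** In Sections 3.4.2.1 and 5.6.3, state that time to CR, its cumulative incidence at Days 28 and 56, and the Cox comparison use only the visits common to both arms: Days 6, 14, 21, 28, 35, 42, 49 and 56. Date a CR at the nominal visit day. For Day 6, use in both arms the staging closest to Day 6 within plus or minus 3 days; if there is none, treat that visit as missing. Keep the other infusion-day stagings for a descriptive T-Guard summary. An interval-censored analysis would be a reasonable sensitivity analysis.

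The cost is about a sentence in each section, with no new visits or data. The downside is that a T-Guard CR first seen before Day 6 is dated at the next common visit, so very early responses appear only in the descriptive summary. The simulated correction used exact visit days; the version with windows and nominal dating was not simulated.
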